1. BACKGROUND AND RATIONALE

1.1. Disease Background and Introduction

Pancreatic cancer continues to be a very lethal disease. It was estimated that in 2021, 60,430 Americans (31,950 men and 28,480 women) would be diagnosed with pancreatic ductal adenocarcinoma (PDA), and 48,220 will die from the disease. Pancreatic cancer accounts for about 3% of all cancers in the US and about 8% of all cancer deaths (Siegel et al. 2021).

Furthermore it is projected that by 2030, PDA will be the second leading cause of death from cancer in the US. Worldwide, PDA is the twelfth most common cancer, accounting for an estimate of > 300,000 deaths a year (Rahib 2014).

Detection of pancreatic cancer has been notoriously very late in the disease and therefore the 5-year survival rate is only 9%. Right now, the only potential cure for pancreatic cancer is surgical resection (if the disease is caught early). However only 10-20% of PDA patients are diagnosed with localized, surgically resectable disease. Even with the advances made over the past decade in the surgical resection of PDA, the 5- year survival after resection and adjuvant chemotherapy approaches 30% (Strobel 2019), and unfortunately most (~ 80%) have reoccurrence of their cancer within 2 years of resection, and those reoccurrences are almost universally fatal (Kleef 2016).

The prognosis for this disease is poor despite diagnostic progress and new chemotherapeutic regimens. Current treatment regimens for advanced PDA although offering modest improvements in progression-free survival (PFS) and overall survival (OS), are clearly inadequate in achieving long term survival in these patients.

Additional treatment strategies are desperately needed. In this study we propose a combination of two commercially available drugs a type I½ RAF inhibitor and a type II RAF inhibitor. As will be seen below this approach is based on some very solid science.

It has been established that 90% of pancreatic cancer patients harbor somatic oncogenic point mutations in KRAS (90%). The oncogenic KRAS mutation has been shown to be the major event in pancreatic cancer; it confers permanent activation of the KRAS protein, which acts as a molecular switch to activate various intracellular signaling pathways and transcription factors inducing cell proliferation, migration, transformation and survival.

The presence of mutated KRAS correlates with a worse prognosis for patients with pancreatic cancer whether or not they undergo surgical resection.

The RAS/RAF/MEK/extracellular signal-related kinase (ERK) pathway is pivotal for cell proliferation and survival and is frequently hyperactivated in tumors. Virtually all pancreatic cancers are KRAS mutated and therefore that pathway is a prime target for

drug development. Clinically used RAF inhibitors are ineffective in RAS mutant tumors because they enhance homo- and heterodimerization of RAF kinases, leading to paradoxical activation of ERK signaling. We built a next-generation mechanistic dynamic model to analyze combinations of structurally different RAF inhibitors, which can efficiently suppress MEK/ERK signaling (Kholodenko, 2015 and Rukhlenko 2018). This rule-based model of the RAS/ERK pathway integrates thermodynamics and kinetics of drug-protein interactions, structural elements, posttranslational modifications, and cell mutational status as model rules to predict RAF inhibitor combinations for inhibiting ERK activity in oncogenic RAS and/or BRAFV600E backgrounds. Predicted synergistic inhibition of ERK signaling was corroborated by experiments in mutant NRAS, HRAS, and BRAFV600E cells, and inhibition of oncogenic RAS signaling was associated with reduced cell proliferation and colony formation.

1.2. Rationale of Clinical Trial

We lost a dear friend, [name], an incredible microbiologist to advanced pancreatic cancer at the young age of 44. [name]'s colleagues, caregivers and friends (some listed here as coinvestigators,) who are experts in Systems Biology and Advanced Analytics, have banded together to provide the best possible fresh, systems-based science to attack pancreatic cancer.

As an overview, this study aims to combine two RAF inhibitors (RAFi) to suppress oncogenic RAS signaling to ERK and overcome the notorious resistance to RAFi caused by RAF dimerization (Kholodenko 2015; Rukhlenko et al., 2018). This is an entirely new approach against RAS mutated pancreatic cancer.

1.3. Study Agent(s) Background and Associated Known Toxicities

1.3.1. Vemurafenib

Vemurafenib is a type I½ RAF inhibitor. Vemurafenib is also an orally available inhibitor of some mutated forms of BRAF serine-threonine kinase, including BRAF V600E. Vemurafenib inhibits other kinases in vitro such as; CRAF, ARAF, wild-type BRAF, SRMS, ACK1, MAP4K5, and FGR at similar concentrations. At steady state, Vemurafenib exhibits linear pharmacokinetic within the 240 mg to 960 mg dose range.

There has been a tremendous amount of clinical experience with Vemurafenib. The most common adverse events include (≥30%): arthralgias, rash, alopecia, fatigue, photosensitivity reactions, nausea, pruritus and skin papillomas. Special precautions from the package insert include new primary cutaneous malignancies, new non-cutaneous squamous cell carcinomas, tumor promotion in BRAF wild-type melanoma patients, serious hypersensitivity reactions (anaphylaxis and Drug Reaction with Eosinophilia and Systemic Symptoms - DRESS syndrome), Stevens-Johnson syndrome and toxic epidermal necrolysis, QT prolongation, hepatotoxicity, photosensitivity (advise patients to avoid sun exposure), uveitis, harm to the fetus, radiation sensitization and recall, and

renal failure. Vemurafenib is currently approved for patients with BRAF V600E mutated melanoma as well as for patients with BRAF V600E mutated Erdheim-Chester disease.

1.3.2. **Sorafenib**

Sorafenib is a kinase inhibitor that inhibits multiple intracellular (CRAF, BRAF and mutant BRAF) and many surface kinases (KIT, FLT3, RET, RET/PTC, VEGFR-1, VEGFR-2, VEGFR-3 and PDGFR- β). It is currently FDA approved for the treatment of patients with hepatocellular carcinoma, advanced renal cell carcinoma and locally recurrent or metastatic, progressive differentiated thyroid carcinoma refractory to radioactive iodine treatment. Sorafenib is a type II BRAF kinase inhibitor (traps their target kinases in an inactive so-called DFG-out state occupying a hydrophobic pocket adjacent to the ATP binding site (Kufareva and Abagyan 2008). The agent has had very extensive clinical trials. No trials with Sorafenib as a single agent in patients with advanced pancreatic cancer have been reported. However, Sorafenib has been added to a gemcitabine+cisplatin combination in patients with advanced pancreatic cancer with no indication for improving the response rate or median progression free survival over what was achieved with chemotherapy alone.

A single arm phase II trial by Kindler and colleagues (Kindler 2012) of gemcitabine+sorafenib also didn't appear promising. However, the hypothesis to be tested in the present study is that the addition of this type II kinase inhibitor to the type I $\frac{1}{2}$ kinase inhibitor Vemurafenib will produce responses in patients. This type of design is based on the very solid science of Kholodenko (2015) and Rukhlenko et al (2018).

Sorafenib's most common adverse reactions include: diarrhea, fatigue, infection, alopecia, hand-foot syndrome, rash, weight loss, anorexia, nausea, gastrointestinal and abdominal pain, hypertension and hemorrhage. The most dangerous of these include: cardiac ischemia (2.7%), bleeding from varices (2.4%), and hypertension (9.4%) (need to take BP weekly for the first 6 weeks). The rash and hand-foot reactions are generally grade 1-2. Rare events include: gastrointestinal perforation, wound healing complications, QT interval prolongation, a 0.06% incidence of hepatic failure and death, and impairment of thyroid stimulating hormone suppression in patients with Differentiated Thyroid Carcinoma. Patients can experience a rise in amylase or lipase (without pancreatitis) and hypophosphatemia (13%), anemia (44%), thrombocytopenia (12%), hypocalcemia (12%) and hypokalemia (5%).

1.4. **Clinical Experience with Reported Phase I Trial with Vemurafenib + Sorafenib**

Preclinical experiments with Vemurafenib plus Sorafenib in a Vemurafenib resistant melanoma cell line demonstrated a synergistic effect of Sorafenib+Vemurafenib (Srivastava and Moorthy, 2019). The MD Anderson team (Kato et al, 2015) have reported an initial phase I clinical trial of Vemurafenib plus Sorafenib to overcome BRAF resistance (NCT0153136). They established the safe doses in this heavily treated population (76% had had prior BRAF or MEK inhibitors). Their MTD was 720mg PO BID of Vemurafenib

2. HYPOTHESIS

The addition of a type I½ RAF inhibitor to a type II RAF inhibitor will have clinical activity against KRAS mutated advanced pancreatic cancer.

3. STUDY OBJECTIVES

3.1. Primary Objectives

To determine the efficacy (disease control rate- CR+PR+ Stable at 16 weeks) of the combination of the type I½ RAF inhibitor (RAFi) Vemurafenib in combination with the type II RAFi Sorafenib in patients with advanced KRAS mutated refractory pancreatic cancer.

[Note: Type I inhibitors bind to the active protein kinase conformation (DFG-ASP “in” αC helix “in”). Type I½ inhibitors bind to a DFG-ASP “in” and αC helix “out” inactive conformation. Type II RAF inhibitors trap kinases in the DFG-ASP “out” αC helix “in” inactive conformation (Roskowski, 2016, Rukhlenko 2018)].

3.2. Secondary Objectives

- To confirm the safety of giving Vemurafenib + Sorafenib to patients with advanced pancreatic cancer.
- To determine the clinical activity of Vemurafenib + Sorafenib as defined Progression free survival (PFS) and Overall survival (OS) rate.
- To utilize circulating tumor DNA (ct DNA) in plasma to give qualitative (mutations) and to some extent quantitative (amount of ct DNA) information

regarding BRAF and KRAS. This will be measured at baseline and just before each cycle

- To measure phospho ERK and phospho AKT in plasma samples to determine if the treatment has hit the intended target (Takano et al. 2010, Petricoin 2009). This will be measured at baseline and just before each cycle.

3.3. Exploratory Objectives

- To evaluate changes in phospho ERK and phospho AKT in tumor tissue.

3.4. Endpoints

3.4.1. Primary Endpoint

- Disease control rate (defined as CR+PR+SD x16 weeks) using RECIST criteria.

3.4.2. Secondary Endpoint

- Safety of giving Vemurafenib + Sorafenib in this population of patients
- Progression free survival
- Overall survival
- Identify whether or not the drug combination resulted in changes in plasma free DNA mutated KRAS, BRAF, phospho ERK, phospho AK

3.4.3. Exploratory Endpoint

- Changes in phospho ERK and phospho AKT in tumor tissue

4. STUDY POPULATION

4.1. Inclusion Criteria

1. Be able to understand and be willing to sign the written informed consent for the trial. A signed informed consent form must be appropriately obtained prior to the conduct of any trial-specific procedure.
2. Be ≥ 18 years of age on day of signing informed consent.
3. Histologically confirmed cancer of the pancreas (KRAS mutated) with metastases and progression on at least ≥ 2 prior treatment regimens for their disease.
4. Known mutation status of KRAS and BRAF kinases. For those patients in which this has not previously been determined, the patient must have an archival tumor specimen (primary or metastatic stie) available to submit to confirm KRAS and BRAF status.
5. Have a performance status of 0 or 1 on the ECOG performance scale.
6. Demonstrate adequate organ function as defined below:
 - a. Absolute neutrophil count $\geq 1,500/\text{mm}^3$
 - b. Platelet concentration $\geq 60 \times 10^9/\text{L}$

- c. Hemoglobin ≥ 8.5 g/dL. Criteria must be met without erythropoietin dependency and without packed red blood cells (pRBC) transfusion within the last 2 weeks.
- d. Serum creatinine $< 1.5 \times$ institutional ULN.
- e. Total bilirubin ≤ 2.5 mg/dL
- f. Alanine aminotransferase (ALT) and Aspartate aminotransferase (AST) $< 5 \times$ ULN
- g. Prothrombin time (PT) ≤ 60 seconds or International Normalized Ratio (INR) ≤ 2.3
- 7. Female participants of childbearing potential must have a negative serum pregnancy test performed within 24 hours prior to receiving first dose of trial medication. Post-menopausal women (defined as no menses for at least 1 year) and surgically sterilized women are not required to undergo a pregnancy test.
- 8. A female participant is eligible to participate if she is not pregnant, not breastfeeding, and at least one of the following conditions applies:
 - a. Not a woman of childbearing potential (WOCBP)
 - OR
 - b. A WOCBP who agrees to follow the contraceptive guidance during the treatment period and for at least 30 days after the last dose of trial treatment.
- 9. Male participants must agree to use contraception during the treatment period and for at least 30 days after the last dose of trial treatment and refrain from donating sperm during this period.
- 10. Patient must have QTC of ≤ 500 ms.
- 11. Subject must be able to swallow and retain oral medication.
- 12. **Measurable disease per RECIST 1.1**

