Number of Patients: Between 7 and 12 evaluable patients In the first stage 7 evaluable patients will be accrued. If there are zero patients with disease control (CR+ PR +Stable at 16 weeks) in these first 7 evaluable patients, the study will be stopped. Otherwise, 5 additional evaluable patients will be accrued for a total of 12 evaluable patients. An evaluable patient is defined as one that receives any number of doses of both agents (Vemurafenib + Sorafenib) and has a scan after at least 2 cycles of treatment.
Name & Dose of Drugs: 
 Vemurafenib will be given 480 mg PO BID daily x 28 days = 1 cycle Dose level -1 will be 240 mg PO BID Sorafenib will be given 200 mg PO BID daily x 28 days = 1 cycle (Dose level -1 will be 200 mg PO daily) 
Note: All doses are to be taken without food. Doses can only be taken one hour before or 2 hours after a meal.

Patient Population: Patients with metastatic advanced KRAS mutated refractory pancreatic cancer where the patient has progressed on ≥ 2 prior chemotherapy regimens for their advanced disease.
Endpoints: Primary: disease control rate (defined as CR + PR + Stable at 16 weeks) using RECIST 1.1 criteria. Secondary: 
 Safety of giving vemurafenib + sorafenib in this population of patients Progression free survival (PFS) Overall survival (OS) Identify whether or not the drug combination resulted in changes in plasma free DNA mutated KRAS, BRAF, phospho ERK and phospho AKT 
Exploratory:
 
 Changes in phospho ERK and phospho AKT in tumor tissue.
Inclusion Criteria: 
 Be able to understand and be willing to sign the written informed consent for the trial. A signed informed consent form must be appropriately obtained prior to the conduct of any trial-specific procedure.

2. Be ≥ 18 years of age on day of signing informed consent.
3. Histologically confirmed cancer of the pancreas (KRAS mutated) with metastases and progression on at least ≥ 2 prior treatment regimens for their disease.
4. Known mutation status of KRAS and BRAF kinases. For those patients in which this has not previously been determined, the patient must have an archival tumor specimen (primary or metastatic site) available to submit to confirm KRAS and BRAF status.
5. Have a performance status of 0 or 1 on the ECOG performance scale.
6. Demonstrate adequate organ function as defined below:

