4.2. Exclusion Criteria

- 1. Is currently participating and receiving trial therapy or has participated in a trial of an investigational agent and received trial therapy or used an investigational device within 2 weeks of the first dose of this trials' treatment.
- 2. Has had prior chemotherapy, targeted small molecule therapy, or radiation therapy within 2 weeks prior to Cycle 1/Day 1 or who has not recovered (i.e. NCI-CTC AE Version 5.0 \leq Grade 1 at the time of signing informed consent) from adverse events due to a previously administered agent(s).

Note: Patients with \leq Grade 2 neuropathy and \leq Grade 2 alopecia are an exception to this criterion and may qualify for the trial.

- 3. Previous BRAF inhibitor use such as vemurafenib, GSK2118436 or sorafenib.
- 4. If patient received major surgery, and has not yet recovered adequately from the toxicity and/or complications from the intervention prior to starting therapy.
- 5. Previously untreated or concurrent cancer that is distinct in primary site or histology from pancreatic cancer except cervical cancer in-situ, treated basal cell carcinoma, or superficial bladder tumor. Subjects surviving a cancer that was curatively treated and without evidence of disease for more than 3 years before

study entry. All cancer treatments must be completed at least 3 years prior to study entry (i.e., signature date of the informed consent form).

6. Has known active central nervous system (CNS) metastases and/or carcinomatous meningitis. Patients with previously treated brain metastases may participate provided they are stable (without evidence of progression by imaging for at least four weeks prior to the first dose of trial treatment and any neurologic symptoms have returned to baseline), have no evidence of new or enlarging brain metastases, and are not using steroids for at least 7 days prior to trial treatment. This exception does not include carcinomatous meningitis, which is excluded regardless of clinical stability.
7. Uncontrolled hypertension (systolic pressure >140 mm Hg or diastolic pressure > 90 mm Hg [NCI-CTCAE v5.0] on repeated measurement) despite optimal medical management.
8. Active of clinically significant cardiac disease including:
 - a. Congestive heart failure New York Heart Association (NYHA) > Class II. (Appendix D)
 - b. Active coronary artery disease (CAD)
 - c. Cardiac arrhythmias requiring anti-arrhythmic therapy other than beta blockers or digoxin.

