 - d. Unstable angina (anginal symptoms at rest), new-onset angina within 3 months before randomization, or myocardial infarction within 6 months before randomization.
9. Has history of (non-infectious) pneumonitis that required steroids or current pneumonitis.
10. Has an active infection requiring systemic therapy.
11. Evidence or history of bleeding diathesis or coagulopathy
12. Patient with any pulmonary hemorrhage/bleeding event of NCI-CTCAE v5.0 ≥ Grade 2 within 4 weeks before initiating study treatment; any other hemorrhage/bleeding event of NCI-CTCAE v5.0 ≥ Grade 3 within 4 weeks before initiating study treatment.
13. Patient with thrombotic, embolic, venous, or arterial events, such as cerebrovascular accident (including transient ischemic attacks) within 6 months of informed consent.
14. Presence of a non-healing wound, non-healing ulcer, or bone fracture.
15. History of organ allograft (including corneal transplant).
16. Known or suspected allergy or hypersensitivity to any of the study drugs (sorafenib, and or vemurafenib) study drug classes, or excipients of the formulations given during the course of this trial.
17. All patients with known diagnosis of Neurofibromatosis Type 1 or other known RAS-opathies
18. Patients with uncontrolled seizures
19. Treatment with medications that have known risk of QTc interval prolongation or Torsades de Pointe (TdP) within 14 days or 5 half-lives before dose of either drug is given in this study and for the duration of the study. Refer to Appendix E1 for medications with a known risk of TdP.

20. Treatment with a strong or moderate CYP3A inducers (e.g, phenytoin, carbamazepine, phenobarbital, St. John's Wort [*hypericum perforatum*], dexamethasone at a dose of greater than 16 mg daily, or rifampin [rifampicin], and/or rifabutin) or inhibitors within 28 days before dose of either drug is given in this study and for the duration of the study. Refer to Appendix G.
21. Malabsorption or other significant bowel or stomach resections
22. Has a history or current evidence of any condition, therapy, or laboratory abnormality that might confound the results of the trial, interfere with the patient's participation for the full duration of the trial, or is not in the best interest of the patient to participate, in the opinion of the treating investigator.
23. Has known psychiatric or substance abuse disorders that would interfere with cooperation with the requirements of the trial.

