6. STUDY PROCEDURES

6.1. Screening / Baseline Procedures

Assessments performed exclusively to determine eligibility for this study will be done only after obtaining informed consent. Assessments performed for clinical indications (not exclusively to determine study eligibility) may be used for baseline values even if the studies were done before informed consent was obtained.

All screening procedures must be performed within 28 days prior to initiated study treatment unless otherwise stated. The screening procedures include:

- Informed Consent
- Medical History -To include concurrent baseline conditions (using NCI CTCAE, version 5.0), prior cancer therapy (including documentation of prior surgery, adjuvant or neoadjuvant chemotherapy and radiotherapy).
- ECOG Performance Status (Appendix B)
- Review inclusion / exclusion criteria
- Vital Signs (blood pressure, pulse, respiratory rate, and temperature)
- Complete physical examination including height (cm) and weight (kg)
- Concomitant medication notation to include all medications taken in the last 30 days
- Hematology: CBC with differential and platelet count
- Serum chemistries: glucose, creatinine, BUN, total bilirubin, AST, ALT, alkaline phosphatase, albumin, LDH, total protein, and electrolytes (sodium, potassium, chloride, CO₂, magnesium, calcium). In patients with known Gilbert's syndrome, it is recommended to perform a direct bilirubin and indirect bilirubin. Calculate creatinine clearance (the Cockcroft-Gault equation may be used to calculate the creatinine clearance at any of the time points in this protocol)
- Coagulation: PT, INR
- CA19-9 (or CA 125, or CEA if not expressers of CA 19-9)
- Serum pregnancy test for WOCBP within 72 hours prior to the first dose of study treatment.
- Electrocardiogram (ECG)
- Computed tomography (CT) / magnetic resonance imaging (MRI) scan to document disease status (including chest, abdomen, pelvis, and other regions as clinically indicated. In addition, brain scan is required to exclude brain metastases if clinically indicated only. If a CT scan was taken within 28 days prior to first dose, a new scan is not necessary. (RECIST 1.1 criteria Section 7.1)
- Blood for correlative analysis - 3 X 10 mL

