11.3.4. Statistical Analysis

The primary efficacy analysis will focus on the disease control rate (CR + PR + SD at 16 weeks). Secondary endpoints include progression-free survival (PFS) and overall survival (OS). The efficacy analysis will only be conducted on patients who have received any number of doses of both agents (vemurafenib + sorafenib) and have a scan after at least 2 cycles of treatment.

Objective responses will be evaluated using the Response Evaluation Criteria In Solid Tumors 1.1 (RECIST 1.1). Changes (i.e. improvements) in tumor measurements from baseline values will be assigned a status of CR or PR or SD. Objective response measurements will comprise the sum of CR plus PR. The overall response rate, as well as the rates for the individual categories of response (i.e. CR, PR, SD, and PD), will be estimated by the percentage of patients achieving these criteria with exact 95% binomial confidence intervals.

Progression-free survival is defined as the interval from the date of study treatment initiation (C1/D1) to the earliest date of documented evidence of recurrent or progressive disease, or the date of death due to any cause, whichever occurs first. Overall survival will be measured from the date of study treatment initiation (C1/D1) to the date of death

due to any cause, or the date of last contact (censored observations). For the estimation of progression-free and overall survival a Kaplan-Meier analysis will be performed.

Longitudinal measurements of circulating tumor DNA (ctDNA) and phospho ERK will be visualized using plots for each evaluable patient. These measurements will be transformed using a logarithmic transformation, if necessary, to remove skewness. Significant changes across time will be assessed using linear mixed effects models, to account for the correlation among the measurements within an individual. If the observed change is non-linear, nonlinear mixed effects models will be used.

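### Inclusion 3 does not require progression on or after the most recent regimen, so in patients with three or more prior regimens carried-over stable disease can count as 16-week disease control

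*Combined protocol and SAP*

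**What the plan says.** Section 4.1, item 3, repeated in the synopsis, admits patients "with metastases and progression on at least ≥ 2 prior treatment regimens for their disease". The trial schema and the synopsis population statement describe the disease as "refractory pancreatic cancer where the patient has progressed on ≥ 2 prior chemotherapy regimens for their advanced disease". Both set a minimum number of failed regimens. Neither says where in the sequence the failures must fall.

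The other criteria that bear on disease status at entry are:
- Section 4.2, item 2, excludes a patient who "Has had prior chemotherapy, targeted small molecule therapy, or radiation therapy within 2 weeks prior to Cycle 1/Day 1", or who has not recovered to Grade 1 or better at consent (Grade 2 neuropathy and alopecia excepted).
- Section 4.1, item 12, asks for "Measurable disease per RECIST 1.1".
- Section 6.1 says of baseline imaging: "If a CT scan was taken within 28 days prior to first dose, a new scan is not necessary".
- Section 4.2, item 22, excludes a patient who "Has a history or current evidence of any condition, therapy, or laboratory abnormality that might confound the results of the trial", in the treating investigator's opinion.

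On the endpoint, section 11.3.4 says: "The primary efficacy analysis will focus on the disease control rate (CR + PR + SD at 16 weeks". Sections 3.1, 3.4.1 and 7.1 agree that stable disease counts. Section 11.1 describes an open-label, single-arm trial. Section 11.2 sets a 5% null, a stop at 0 of 7 and rejection at 3 or more of 12, with a stated type I error of 0.0188 and power of 0.9077 at 40%. Section 11.4 repeats the seven-patient stop in terms of disease control.

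The synopsis, under Statistical Methods, also describes a rule adopted after a May 2022 note to file: 5 patients, then 7 more, counting only PR or CR.

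**The concern.** Stable disease at 16 weeks is informative in a single-arm trial to the extent that the tumour would otherwise have progressed. If a patient's disease was already being held when the last regimen stopped, stability at 16 weeks may reflect that regimen or slow-growing disease. Without a control arm, the trial cannot tell this apart from an effect of the study drugs.

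The criteria leave room for such a patient: progression on regimens 1 and 2, stable disease on regimen 3, regimen 3 stopped for toxicity or by choice, toxicity resolved, and more than two weeks elapsed. Because the washout is 14 days and the baseline scan may be 28 days old, the scan can even date from while regimen 3 was still being given.

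Three features make this matter:
- The bar is low in absolute terms: three successes in twelve.
- Patients without a scan after at least two cycles are replaced, with up to 24 enrolled to reach 12. Quiescent disease plausibly makes a patient more likely to reach that scan.
- The medical history items in section 6.1 and Appendix A do not name response to, or date of progression on, the last regimen. The question may not be answerable afterwards.

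**Working it through.** **1. Does any criterion close the gap?** Take a patient with three prior regimens: progression on the first two, stable on the third, now off it for more than 14 days.

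| Criterion | Result |
|---|---|
| Inclusion 3: progression on at least 2 regimens | met by regimens 1 and 2 |
| Inclusion 12: measurable disease | can be met with stable disease |
| Exclusion 2: 2-week washout and recovery to Grade 1 or better | can be met; not automatic if stopped for toxicity |
| Exclusion 22: investigator's opinion on confounding | discretionary; no progression rule |
| Refractory, in the objectives and population statement | not a numbered criterion; explained only by the count of two |

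The patient is eligible. With exactly two prior regimens, progression on at least two means both failed, including the latest, so the gap does not arise.

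**2. Reproduce the plan's figures (section 11.2).** With X successes in the first 7 and Y in the next 5,

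P(reject) = Σ (x = 1 to 7) P(X = x) · P(Y ≥ max(0, 3 − x)).

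At p = 0.05:
- x = 1: 0.25728 × 0.02259 = 0.00581
- x = 2: 0.04062 × 0.22622 = 0.00919
- x ≥ 3: 0.00376
- sum: 0.01876, the stated 0.0188.

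At p = 0.40 the same sum is 0.90767, the stated 0.9077. Both figures are right.

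**3. Effect of k such patients when the drugs are inactive.** Inputs not in the documents, so assumed: exactly k = 1, 2 or 3 of the 12 entered without progression on the last regimen; each has probability q of being stable at 16 weeks anyway; the other 12 − k are at the 5% null. The k patients fall at random across the two stages, with k₁ in the first seven:

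- weight of k₁ = C(7, k₁) · C(5, k − k₁) / C(12, k)
- stage 1 successes = Bin(7 − k₁, 0.05) + Bin(k₁, q)
- stage 2 successes = Bin(5 − k + k₁, 0.05) + Bin(k − k₁, q)
- false success = at least 1 in stage 1 and at least 3 in total.

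Example, k = 2. The weights for k₁ = 0, 1, 2 are 10/66, 35/66 and 21/66, that is 0.1515, 0.5303 and 0.3182.
- q = 0.2: 0.1515 × 0.0453 + 0.5303 × 0.0491 + 0.3182 × 0.0504 = 0.0489
- q = 0.6: 0.1515 × 0.1493 + 0.5303 × 0.1851 + 0.3182 × 0.1875 = 0.1805

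| k of 12 | q = 0.2 | q = 0.3 | q = 0.4 | q = 0.5 | q = 0.6 |
|---|---|---|---|---|---|
| 0 | 0.0188 | 0.0188 | 0.0188 | 0.0188 | 0.0188 |
| 1 | 0.0312 | 0.0396 | 0.0479 | 0.0562 | 0.0645 |
| 2 | 0.0489 | 0.0749 | 0.1054 | 0.1406 | 0.1805 |
| 3 | 0.0722 | 0.1262 | 0.1956 | 0.2810 | 0.3829 |

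**4. After the fix.** Excluding such patients sets k = 0. The 7+5 sample size, 0.0188 and 0.9077 stay as they are.

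**The case against.** Much of the case against limits the point; none of it removes it.

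- **The exposed group is narrow.** It needs three or more regimens, progression on two others, a last regimen stopped for another reason, and recovery to Grade 1 or better. This stands. A reader might infer that any stable patient in the trial is suspect, but the criteria do not support that.
- **The size rests on assumptions.** Nothing in the documents gives k or q. The upper part of the q range begins at the 40% rate that section 11.2 hopes for from an active combination. At q = 0.2 the error stays just below 0.05 with one or two such patients. This stands, and is why the whole range is shown.
- **A larger figure is tempting.** Giving all 12 patients the averaged rate 0.05 + (k/12)(q − 0.05) yields 0.128 to 0.228 for k = 2 and q = 0.4 to 0.6, against 0.1054 to 0.1805 above. That describes a population share, not a known number of patients among twelve, and overstates the error for a fixed count.
- **There are partial safeguards.** The population is called refractory, and Exclusion 22 lets an investigator refuse a patient whose therapy might confound the results. Both help; neither is an enforceable progression rule.
- **The decision rule may be different.** Under the synopsis's 5+7 rule only PR or CR counts, so carried-over stable disease would not change the decision. This stands for that rule. Sections 3, 7.1, 11.2, 11.3.4 and 11.4 nevertheless keep disease control, and the two rules conflict.
- **Current progression is not the only way to make stability informative.** True. Requiring it is good practice, not the repair of an arithmetic error.

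**Conclusion.** The concern holds in limited form. As written, Inclusion 3 admits patients with three or more prior regimens whose disease was not progressing on the latest, and their 16-week stability would count toward a single-arm test with a 5% null and a 3-of-12 cutoff. On the assumptions stated (k fixed, q from 0.2 to 0.6, the rest at 5%, drugs inactive), the chance of false success rises from 0.0188 to 0.0312–0.0645 with one such patient, 0.0489–0.1805 with two and 0.0722–0.3829 with three. Two patients at q = 0.2 already give 0.0489/0.0188 = 2.6 times the stated error.

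Two stronger conclusions do not follow. A reader might infer that the stated 0.0188 is wrong: it reproduces exactly, and what is in doubt is whether 5% describes everyone the criteria admit. A reader might also infer that such patients have been or will be enrolled in these numbers: the documents say nothing on that.

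The result applies to the disease-control rule. Whether that rule or the synopsis's PR/CR rule governs the decision has to be settled in the text. The reported disease control rate is exposed either way. This is an inexpensive improvement that should be made, held with moderate confidence because its size cannot be fixed from the documents.

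**What to change.** - Add to Inclusion 3, in both the synopsis and section 4.1: *and radiographic progression documented on or after the most recent regimen, before Cycle 1 Day 1*.
- Record on the eCRF the date and basis of that progression.
- For patients already enrolled without it, report the disease control rate with and without them.
- Reconcile the 5+7 PR/CR rule in the synopsis with the 7+5 disease-control rule in sections 11.2 and 11.4 and with the endpoint in sections 3, 7.1 and 11.3.4, so that it is clear which decision this bears on.

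The cost is one eligibility clause, one eCRF entry and one extra tabulation. A few patients who stopped their last regimen without progression would wait or not be enrolled. In this population that is a real, if small, cost to those patients and to accrual. Sample size, type I error and power do not change.
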